3.7.3 Secondary Efficacy Analyses

The analyses of the time until catheter removal for any reason and of time until loss of catheter patency will be based on the Full Analysis Population using the log-rank comparison, hazard ratio with 95% confidence interval (active/control), and incidence of the event of interest with 95% CI. For these endpoints, subjects will be considered censored as of their final clinical assessment if the event of interest is not observed. Otherwise, the event time will be the number of days between randomization and the event.

3.7.4 Additional Analyses

The HR for the primary analysis and relative risk for the incidence rates (along with 95% CIs for both) will be presented (tabular summary and graphically using a forest plot) for subgroups formed by the following variables (at baseline):

- age (< 65, ≥ 65 and ≥ 75 years of age)
- race
- sex
- diabetes
- months receiving dialysis (≤12 months vs. > 12 months)
- port location, and
- catheter type

3.8 Analysis of Safety Endpoints

All of the tables described in the following are to be conducted using the Safety Population.

3.8.1 Brief Summary of Treatment Emergent Adverse Events (TEAEs)

Adverse events are defined as treatment emergent if they start or worsen after a subject's first administration of study CLS. A brief summary of TEAEs, serious TEAEs, TEAEs leading to death,

TEAEs leading to drug discontinuation, TEAEs leading to study discontinuation, study drug-related TEAEs, and serious study drug-related TEAEs will be presented by treatment arm and overall. The total number of TEAEs and the number and percentage of subjects with at least one TEAE will be presented summarized by severity and by relationship to study drug for each treatment arm and overall. This information will also be listed.

3.8.2 TEAEs by System Organ Class and Preferred Term

The number and percentage of subjects reporting TEAEs will be tabulated by preferred term and system organ class (SOC) for each treatment group. TEAEs will be classified by SOC and preferred term using the Medical Dictionary for Regulatory Activities (MedDRA). Similar summaries will be produced for SAEs, TEAEs leading to termination, severe TEAEs, and TEAEs with a relationship to the investigational product.

TEAEs will also be summarized by SOC, preferred term, and severity and by SOC, preferred term and relationship to study medication. In the event of multiple occurrences of AEs with the same SOC/preferred term in one subject, the AE will be counted once as the occurrence with the highest severity or closest relationship for the summaries by severity and relationship, respectively.

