
Test product, dose and mode of administration:
 
Neutrolin[®] and the active control will be packaged in identical vials, and will be used as a catheter locking solution for HD catheters in the following manner:
 
 • Day 1 (day of first administration of blinded, randomized therapy): following randomization and entry into the trial, instill CLS following the index HD episode, as described in the protocol; • Subsequent HD sessions: CLS will be removed prior to HD and instilled in the catheter following the HD session, as described in the protocol. 	

Duration of treatment:
 
Subjects are to be followed from randomization until either:
 
 • The development of a CRBSI; • Withdrawal from the study; • Catheter removal; or • The end of the study, whichever occurs first. 
The study has been designed to continue until approximately 56 subjects have experienced a CRBSI. It is expected that some subjects may be treated for 2 years or more.
	

Reference therapy, dose, and mode of administration:
 
Heparin 4,000 USP Units/4mL (1,000 USP Units/mL) as a CLS for the active control.
	

Criteria for evaluation:
 
Primary endpoint: Time to CRBSI:
 
The primary objective of this study is to demonstrate the effectiveness of Neutrolin[®] as a CLS in ESRD subjects undergoing HD treatment using a permanent, cuffed, tunneled
	

Protocol Synopsis	
Name of Sponsor/Company:	CorMedix Inc.
Name of Finished Product:	Neutrolin®
Name of Active Ingredients:	Taurolidine (1.35% (13.5 mg/mL), 3.5% (26.1 mg/mL) citrate and heparin 4,000 USP Units/4 mL (1,000 USP Units/mL))

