
arms subject to the following specifications: testing will be conducted at a 2-sided overall 5% alpha level, Neutrolin[®] is associated with a 55% reduction in the risk (i.e., incidence) of CRBSI relative to the control arm, and one interim analysis will be performed at the midpoint of the trial with adjustment of the alpha level using the method of Pocock. Fifty-six CRBSI events in total will be needed to achieve the desired power, and the event rates will be monitored over the course of the trial to determine the times of the interim and final statistical analyses. It is expected that approximately 900 subjects will be randomized for this trial.
 
Safety analyses
 
The safety information will be presented based upon descriptive analysis characterizing the relative rates of deaths, adverse events, serious adverse events and loss of patency between the treatment arms. The treatment arms will also be evaluated with respect to changes in laboratory parameters.
	

TABLE OF CONTENTS

1.0	LIST OF ABBREVIATIONS AND DEFINITIONS OF TERMS	13
2.0	INTRODUCTION.....	15
2.1	Clinical Need for Prevention of Catheter-Related Bloodstream Infections.....	15
2.2	Background on Catheter Lock Solutions	16
2.3	Overview and Rationale for Use of Neutrolin® as a Catheter Lock Solution	20
2.4	Safety of Neutrolin®	22
2.5	Rationale for the Formulation of Neutrolin®	24
3.0	STUDY OBJECTIVES.....	25
3.1	Primary Objectives	25
3.2	Safety Objectives.....	25
3.3	Primary Endpoint	25
4.0	INVESTIGATIONAL PLAN	27
4.1	Overall Study Design and Plan.....	27
4.2	Discussion of Study Design	28
5.0	SELECTION OF STUDY POPULATION.....	29
5.1	Inclusion Criteria	29
5.2	Exclusion Criteria	30
5.3	Study Completion, Early Withdrawal, New Catheter Placement.....	31
6.0	STUDY TREATMENTS	33
6.1	Identity of Investigational Products	33
6.2	Blinding	33
6.3	Treatments to Be Administered	33
6.4	Method of Assigning Subjects to Treatment Group	34
6.5	Selection of Neutrolin® Composition and Control	34
6.6	Selection and Timing of the Catheter Lock Solution	34
6.7	Prior and Concomitant Therapy/PROCEDURES.....	34
6.8	Standard of Care for Prevention of CRBSI.....	35
6.9	Standard of Care for Hemodialysis	35
6.10	Treatment Compliance.....	35
6.11	Investigational Product Accountability	36
7.0	EFFECTIVENESS AND SAFETY VARIABLES	37
7.1	Schedule of Assessments.....	37
7.2	Screening/Baseline Assessments	44

7.3	Effectiveness Measurements	45
7.4	Safety Measurements	47
7.5	Appropriateness of Measurements	52

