1.5 Sample Size

This trial has been designed to achieve 80% power for the comparison between treatment arms subject to the following specifications: testing will be conducted at a 2-sided overall 5% alpha level using the log-rank test, Neutrolin is associated with a 55% reduction in the risk of CRBSI relative to the control arm, a 1 to 1 ratio will be used for the allocation of subjects to treatment arms, and one interim analysis will be performed at the midpoint of the trial with adjustment of the alpha level using the method of Pocock. Fifty-six CRBSI events in total will be needed to achieve the desired power. The interim analysis will be conducted based on the first 28 CRBSIs. The total sample size is expected to be approximately 900 subjects.

2 Statistical Methods

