2.4 Statistical Assessment of the Trial Objectives

2.4.1 Primary Endpoint Analysis

The primary analysis will be conducted using a log-rank test for the time to CRBSI at an overall 2-sided 5% alpha level. The null hypothesis is that there is no difference in the hazard rates of CRBSI over time between the two treatments. The time until CRBSI will be calculated as the number of days post randomization until the occurrence of a CAC-adjudicated CRBSI or the subject is censored. Subjects without a CRBSI will be treated as censored in this analysis if the catheter is removed for reasons other than CRBSI (e.g., catheter removed because no longer required) or follow-up is completed in the absence of CRBSI. Because an interim analysis for efficacy will be performed, the method of Pocock will be used to control the overall alpha level. Therefore, the nominal significance level at the interim and final statistical analyses for the primary efficacy endpoint will be 0.0294.

The primary analysis will be based upon the Full Analysis Population. While testing will be based upon the log-rank test, the estimated treatment effect will be the difference between treatment groups in the incidence rate of CRBSI, calculated as the number of subjects with a CRBSI divided by the number of catheter-days of follow-up over subjects (follow-up will be based upon the same time as used for the log-rank test). The rates will be presented as the event rates per 1000 catheter-days with a 95% confidence interval for the purpose of comparison of rates between the treatments. This confidence interval will be derived assuming that the number of catheter-days until CRBSI follows an exponential distribution.

In the primary analysis of the primary endpoint, cases considered to be indeterminate by the CAC will be excluded. A sensitivity analysis will be performed in which cases considered to be indeterminate will be treated as CRBSI events.

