3.1 General Conventions

Unless otherwise stated, summary statistics including the number of subjects (n), mean, standard deviation, median, minimum and maximum will be presented for continuous variables. Minimum and maximum values will be presented to the same decimal precision as the raw values, the mean and median

values to one more, and the standard deviation, to two more decimal places than the raw values. For categorical variables, per category, the absolute counts (n) and percentages (%) of subjects with data, and if appropriate, the number of subjects with missing data, will be presented. Percentages will be presented to one decimal place.

For efficacy and safety analyses, age will be calculated relative to the date of randomization.

For adverse events reported on a per-subject basis, medical history and concomitant medications, the denominator for the percentage calculation will be the number of subjects in the analysis population and in the subgroup of interest at risk in each treatment arm.

All p-values will be rounded to 4 decimal places. If a p-value is less than 0.0001 it will be displayed as “< 0.0001”.

All non-efficacy summary tables will use either the Randomized Population or the Safety Population. All efficacy summary tables will use the Full Analysis Population unless specified otherwise. Summaries will be provided by treatment group.

Not all data collected (e.g., vital signs at each dialysis visit) will be summarized or listed. All such data will be included in the appropriate analysis file for display and summarization as needed during the preparation of the clinical study report (i.e., ad hoc displays).

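### Adverse events are summarised without a time-at-risk denominator although follow-up is open-ended and ends at outcomes that treatment may affect; the expected distortion is small but its direction is not fixed

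*SAP*

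**What the plan says.** Follow-up runs from randomization to CRBSI, catheter removal, withdrawal or study end, whichever is first (Protocol Synopsis, Duration of treatment; Protocol 4.1). There is no fixed duration: "It is expected that some subjects may be treated for 2 years or more". Adverse events are collected until 28 days after the last lock is removed (Protocol 7.4.1).

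The Protocol Synopsis describes the safety analysis as "descriptive analysis characterizing the relative rates of deaths, adverse events, serious adverse events and loss of patency between the treatment arms". In SAP 3.8.2, "The number and percentage of subjects reporting TEAEs will be tabulated by preferred term" and by system organ class. SAP 3.8.1 gives the total number of TEAEs and the number and percentage of subjects affected. SAP 3.1 fixes the denominator for events reported per subject: "the denominator for the percentage calculation will be the number of subjects in the analysis population". That sentence goes on to mention subjects at risk in a subgroup, but this is still a count of subjects, not of time.

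SAP 2.2 and 3.4 summarise duration of exposure by arm in a separate table. By contrast, CRBSI, catheter removal and loss of patency are all reported per 1,000 catheter-days (SAP 2.4.1 and 2.4.2). Section 1.2 of the SAP addendum bases the primary safety analyses on data through the last patient's last visit and otherwise follows the SAP, so the same tables carry over.

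**The concern.** A percentage of subjects compares risk fairly between arms when both arms are watched for about the same time. Here the watching stops at the efficacy event and at catheter removal. The plan assumes that treatment more than halves the first, and formally tests the second as a secondary endpoint. The design thus allows for unequal observation time, and the efficacy tables handle this with person-time while the adverse event tables do not.

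At stake is the safety objective in Protocol 3.2, which is to describe any added risk of Neutrolin. If one arm is observed longer, its crude percentages rise even when the hazard of an adverse event is identical. If it is observed for a shorter time, the same tables can mask a real excess. The percentages alone do not show which has happened.

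**Working it through.** **1. The plan's own figure.** Inputs from SAP 1.5 and 2.4.1: "This trial has been designed to achieve 80% power"; "Neutrolin is associated with a 55% reduction in the risk of CRBSI relative to the control arm", so HR 0.45; "testing will be conducted at a 2-sided overall 5% alpha level using the log-rank test"; 1:1 allocation; and "the nominal significance level at the interim and final statistical analyses for the primary efficacy endpoint will be 0.0294".

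- Events for a single look: 4 × (1.960 + 0.842)² / (ln 0.45)² = 4 × 7.849 / 0.6376 = 49.2, rounded up to 50.
- Two-look Pocock boundary with the interim at half the events: critical value 2.178, inflation factor 1.110.
- 50 × 1.110 = 55.5, rounded up to 56. Power at 56 events is 81.0%.

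The 56 events reproduce. They amount to 56/900 = 6.2% of planned subjects whose observation ends at CRBSI.

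**2. Model.** The documents give no accrual period, design control rate or rate of other exits, so these are assumed: constant hazards, uniform entry over S = 730 days with closure at day 730, mean 180 days to any exit other than CRBSI, the same adverse event hazard θ = 2 per 1,000 days in both arms, and a 28-day tail for everyone. With η the total exit hazard:

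- Mean follow-up = (1/η) × [1 − (1 − e^(−ηS))/(ηS)].
- Crude AE proportion = 1 − e^(−28θ) × [η/(η+θ) + m·θ/(η+θ)], where m = (1 − e^(−(η+θ)S))/((η+θ)S).

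A control CRBSI hazard of 0.674 per 1,000 days (Neutrolin 0.45 × 0.674 = 0.303) gives the planned events: 450 × 0.000674 × 125.6 = 38.1 and 450 × 0.000303 × 131.3 = 17.9, total 56.0.

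**3. CRBSI truncation alone (other exits equal).**

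- Control: η = 0.005556 + 0.000674 = 0.006230; mean follow-up 125.6 days; crude AE 24.6%.
- Neutrolin: η = 0.005556 + 0.000303 = 0.005859; mean follow-up 131.3 days; crude AE 25.3%.
- Follow-up ratio 131.3/125.6 = 1.05; with the tail, 159.3/153.6 = 1.04. Crude AE ratio 25.3/24.6 = 1.03.

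Six scenarios were each calibrated to 56 events in 900 subjects (no other exits, or mean 365 or 180 days to other exit; study length 1 or 2 years; different entry patterns). Follow-up is 2.5% to 4.6% longer on Neutrolin (2.3% to 3.7% with the tail). Crude incidence at equal hazard moves as follows:

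| Control | Neutrolin |
|---|---|
| 5% | 5.1–5.2% |
| 20% | 20.4–20.6% |
| 50% | 51.0–51.1% |
| 80% | 80.7–81.3% |

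**4. Other exits unequal.** Same model as step 3, changing only the other-exit hazard on Neutrolin. Control stays at 125.6 days and 24.6%.

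| Other-exit hazard on Neutrolin | Mean follow-up (days) | Follow-up ratio | Crude AE | AE ratio |
|---|---|---|---|---|
| 20% lower | 151.8 | 1.21 | 27.8% | 1.13 |
| equal | 131.3 | 1.05 | 25.3% | 1.03 |
| 6.7% higher | 125.6 | 1.00 | 24.6% | 1.00 |
| 20% higher | 115.5 | 0.92 | 23.3% | 0.95 |

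With a common cutoff of 1 or 2 years instead of staggered entry, a 20% lower hazard gives AE ratios of 1.14 to 1.17, and a 20% higher hazard gives 0.93 to 0.94.

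**5. The alternative measure.** First events divided by time at risk estimates θ in each arm whatever η is. At equal hazard the ratio is 1.00 in every row above.

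**The case against.** The case for leaving the plan alone has real force.

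- **No commitment is broken.** Protocol 9.8.1 itself specifies numbers and percentages of subjects, and the SAP does that. The synopsis refers to relative rates within a descriptive analysis and promises no person-time denominator. This stands: the point is an improvement, not a deviation.
- **The SAP offers partial information.** Event totals and exposure by arm let a reader see an imbalance and form a rough overall rate. Catheter removal and loss of patency already have person-time rates. This narrows the gap to the adverse event tables but does not close it. Exposure duration is not stated to include the 28-day tail, and it cannot give first-event rates by preferred term. The efficacy denominator cannot be borrowed either, because the addendum censors no later than last dose plus 3 days.
- **Exposure-adjusted rates have their own weakness.** They assume a roughly constant hazard. For events that cluster early, longer exposure dilutes the rate. This stands, and is why the percentages must stay.

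A reader might go further and infer that the better-protected arm must be observed longer and will look materially less safe, using the 2 to 5.5 CRBSIs per 1,000 catheter-days in Protocol 2.1. The documents do not support that. Those are background literature rates, not design inputs. With a mean of 180 days to other exit and no cutoff, 2 per 1,000 would produce 450 × (0.002/0.007556 + 0.0009/0.006456) = 182 events, and 5.5 per 1,000 about 363, against 56 planned. Conversely, at those rates 56 events need 56/(0.002 × 0.725) = 38,600 or 56/(0.0055 × 0.725) = 14,000 patient-days, about 43 or 16 days per subject. Nor is the direction assured. Catheter removal, withdrawal, death, transfer and end of dialysis also end follow-up, and step 4 shows that a modest imbalance cancels or reverses the effect. The documents also do not exclude CRBSI from the adverse event tables; if it is counted, control percentages rise.

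**Conclusion.** The gap is real and modest. The plan compares adverse events between arms without a time-at-risk measure in a trial where observation time can depend on treatment. From CRBSI truncation alone, at the design figures and with other exits equal, the distortion is minor: a false ratio of about 1.03 in the worked case, and a shift of at most about 1.3 percentage points at 80% incidence. It becomes material only if catheter removal or other exits differ between arms, and then it can run either way. A 20% difference is an assumption, not a figure from the documents.

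The sizes rest on constant hazards, 56 events in 900 subjects, and assumed accrual and exit rates. The addendum says that the trial stopped after the interim look at 28 events, but gives neither the final event count nor the number randomized, so the actual imbalance cannot be computed from the documents. Nothing here invalidates the safety analysis. It is a low-cost improvement to how that analysis can be read.

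**What to change.** In SAP 3.8.1 and 3.8.2, and in the addendum's safety analyses, keep n (%) and add exposure-adjusted incidence per 1,000 days: subjects with a first event divided by total time from first dose to first event or the end of the 28-day collection window. Define this safety denominator explicitly.

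- For deaths, any TEAE, SAEs and TEAEs leading to discontinuation: rates by arm, with a descriptive rate difference and 95% CI.
- By SOC and preferred term: rates only. Intervals for every term would add many comparisons to a deliberately descriptive analysis.
- When relative rates are described, read the adjusted rates together with the percentages, and do not rest the safety conclusion on either alone. Events with early onset need the percentages as well.

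The cost is a short SAP addition and a few table columns, from dates already collected. No new data or hypothesis tests are needed.

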3.8.3 Clinical Laboratory Tests

Descriptive statistics will be calculated for clinical laboratory tests (hematology, serum chemistry) at applicable visits. Where applicable, changes from baseline will be summarized by treatment group.

3.8.4 Vital Signs

Vital signs, actual values and changes from baseline, will be summarized by treatment group for the monthly visit (note, data summaries for each dialysis visit will not be produced) using descriptive statistics.

3.8.5 Other Safety Analyses

Dialyzer blood flow, time between end of last medication and start of treatment, and spKt/V will be summarized by treatment arm using descriptive statistics for a summary of previous dialysis treatment. Dialyzer blood flow, ESA Dose, IV Iron Dose, and Heparin will be summarized by treatment arm and visit using descriptive statistics for dialysis sessions.

3.8.5.1 Pregnancy

Pregnancies will be summarized by treatment arm. Outcomes will be listed for each pregnancy.

4 Changes to the Protocol-Specified Analyses

The definition of the primary endpoint was revised from the protocol, as per agreement with the FDA. It reflects use of a Clinical Adjudication Committee.

The protocol stated that the number and percentage of subjects who received drug or control at all visits will be presented to summarize compliance and duration of exposure, but this will not be done.

The protocol stated that the primary analysis of the primary endpoint would be repeated using all randomized subjects with available data, but this will not be done.

The protocol stated that physical examination data will be summarized descriptively by treatment group, but this will not be done.

The protocol stated that changes in vital signs parameters from baseline will be summarized across treatment groups at each applicable post-randomization visit, but this will be done only for the monthly visits.

The protocol stated that the number and percentage of subjects with abnormal laboratory results will be provided, but this will not be done.

5 References

Pocock, S.J., Group sequential methods in the design and analysis of clinical trials. *Biometrika*, 1977. 64: 191-199.

Approval Sheet

Product: Neutrolin®
Protocol Number: LOCK-IT-100
Date: January 29, 2018

The individuals signing below have reviewed and approve this statistical analysis plan.

[name]

[name].
Director, Biostatistics
Biostatistical Consulting Inc.

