Taurolidine has been given systemically to humans in doses up to 30 grams per day with no significant adverse outcomes [31]. The concentration of taurolidine in Neutrolin[®] is approximately 400 times less than what has been used previously without safety issues, and considered negligible from a safety perspective. It should not be anticipated that taurolidine at 1.35% poses any risk in case of unintended bolus administration.

As noted previously, citrate is known to chelate calcium, and hypocalcemia is a known risk associated with the use of high concentrations of citrate (30% or greater). 4% citrate (alone) has been demonstrated to be equivalent to heparin as a CLS [29, 30] and is more than 10-fold lower than the concentration issued a warning by the FDA [28]. This low citrate concentration is regarded as safe in case of unintended bolus administration, as the citrate would be expected to rapidly distribute in the extracellular space and be metabolized by the liver within minutes [20]. However, it is possible that mild hypocalcemia symptoms might be seen with rapid flushing of Neutrolin[®], although such use is not anticipated or recommended [38].

When used as a CLS, heparin has the potential to cause a prolongation of clotting times due to inadvertent escape from the catheter at instillation and between dialysis treatments. Depending on the half-life of the heparin used, there could be an increased bleeding risk for 12-24 hours [16]. The heparin concentration in Neutrolin[®] is identical to the concentration currently used in clinical practice (1,000 USP Units/mL). Therefore, the bleeding risk associated with inadvertent systemic administration of Neutrolin[®] should be no greater than current standard of care.

When taurolidine/citrate is used as a CLS for CVCs in other indications where catheter flushing is routine, some subjects have reported an “unusual taste” following infusion, as well as pain with inadvertent injection into a peripheral vein [38].

In studies evaluating the pharmacokinetics of taurolidine given by rapid and high dose peripheral infusion, burning, pain and erythema at the infusion site as well as facial flushing, numbness and pain in the shoulder of the infusion arm have been reported [38]. This is obviously a very different situation from the dosing, site of infusion and intended use compared with Neutrolin®.

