3.2 SAFETY OBJECTIVES

The safety objectives of this study are to characterize any increased risks associated with the use of Neutrolin[®] used as a CLS with respect to adverse events and laboratory assessments as well as catheter removal for reasons other than CRBSI.

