7.4.1 Adverse Events

An AE is any unfavorable or unintended sign, symptom, or disease temporally associated with the use of the investigational drug whether or not considered related to the investigational drug. Collection of AE data will begin after the subject has signed the informed consent document and end 28 days after removal of the last dose of IP. Adverse events may include:

- Objective signs observed by the PI or study personnel
- Subjective or objective signs/symptoms
- Concomitant disease or accidents
- Clinically relevant adverse changes in laboratory parameters observed in a subject in the course of a clinical study
- Pre-existing conditions that worsen in severity or frequency or have new signs/symptoms associated with them.

Other findings related to out-of-range laboratory values, ECGs, vital signs, etc., considered not clinically significant are not to be recorded in the AE CRF page.

Treatment-emergent AEs (TEAE) will be summarized in tables in the final study report. A treatment-emergent adverse event is an AE that starts or worsens after the subject's first administration of investigational product.

An AE is any untoward medical occurrence in a subject or clinical investigation subject administered a pharmaceutical product that does not necessarily have a causal

relationship with this treatment. An AE can therefore be any unfavorable and unintended change in structure, function, signs, or symptoms temporally associated with the use of a medicinal product, whether or not related to the product. Worsening of a pre-existing condition is also considered an AE, as is the discovery of an abnormal finding during a physical examination that was not included in the medical history.

Where there is deterioration in the condition for which the investigational drug is being used, there may be uncertainty as to whether this is normal disease progression or an AE related to the investigational drug administration. If it is felt the investigational drug may have contributed to the deterioration, then this must be treated as an AE related to the investigational drug administration.

Causality Assessment of AEs

For all AEs, the PI will provide an assessment of causal relationship to the investigational drug. The causality assessment must be recorded in the AE CRF.

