9.8.2 Clinical Laboratory Tests

Descriptive statistics will be calculated for clinical laboratory tests (hematology, serum chemistry) at applicable visits. Where applicable, changes from baseline will be summarized across treatment groups. The number and percentage of subjects with abnormal laboratory results will be provided.

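### SAP Section 4 drops, without a reason, the only planned count of subjects with abnormal laboratory results, so out-of-range values that investigators do not report as adverse events go uncounted by arm

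*SAP*

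**What the plan says.** Protocol 3.2 sets the safety objective as describing any added risk "with respect to adverse events and laboratory assessments as well as catheter removal for reasons other than CRBSI". Laboratory assessments thus stand beside adverse events as a component of their own.

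Protocol 9.8.2 plans descriptive statistics, changes from baseline and a third item: "The number and percentage of subjects with abnormal laboratory results will be provided".

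SAP Section 4, which lists departures from the protocol, removes that third item: "the number and percentage of subjects with abnormal laboratory results will be provided, but this will not be done". No reason is given. In the same list, the change to the primary endpoint is explained by agreement with the FDA.

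SAP 3.8.3 keeps the other two items: "Descriptive statistics will be calculated for clinical laboratory tests (hematology, serum chemistry) at applicable visits", with change from baseline where applicable. SAP 3.1 says what descriptive statistics means: "summary statistics including the number of subjects (n), mean, standard deviation, median, minimum and maximum will be presented for continuous variables".

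Addendum 1.2 bases the primary safety analyses on data through the last patient's last visit and refers back to the SAP for how they are done. The count does not return there.

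**The concern.** Hematology and chemistry, including adjusted calcium, are drawn at screening, every four weeks and at the final safety visit (Protocol Table 2). The natural safety question for such data is how many subjects in each arm left the reference range. A mean answers a different question: a small group with a clear deviation hardly moves it.

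Calcium is the obvious example, because the protocol itself raises it. Citrate chelates calcium, the comparator contains no citrate, and Protocol 2.4 says "it is possible that mild hypocalcemia symptoms might be seen with rapid flushing of" the test product. The removal is not confined to calcium, however. Platelets, liver enzymes and every other collected test lose their counts as well.

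At stake is whether the study report can state, by arm and as planned, the share of subjects with out-of-range values. Neither the primary efficacy test nor its error control is affected.

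**Working it through.** **Step 1. What each route to a count provides.**

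| Route | Source | Number of subjects outside limits, by arm? |
|---|---|---|
| Abnormal-result table | Protocol 9.8.2 | Yes, but removed in SAP Section 4 |
| Descriptive statistics and change from baseline | SAP 3.8.3 with 3.1 | No |
| TEAE tables, n and % by preferred term | SAP 3.8.2 | Only for changes recorded as adverse events |
| Ad hoc displays | SAP 3.1 | Possible, none prespecified |

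The SAP contains no shift table, centile or threshold count for any laboratory test. The TEAE route is filtered. Protocol 7.4.3 has the investigator review each central laboratory report and enter clinically relevant changes as adverse events. Protocol 7.4.1 says that out-of-range values "considered not clinically significant are not to be recorded in the AE CRF page". Values in that second group appear in no planned count.

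**Step 2. What the remaining statistics can and cannot show (illustration).** The plan states no figure to reproduce. The only documented input is 450 subjects per arm (Protocol synopsis). All calcium values are assumptions: mean 9.0 mg/dL, SD s = 0.6 or 0.8, low cut-off 7.5, and a share f = 5% of one arm lowered by d = 1.5 mg/dL.

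- Mean shift = −f × d = −0.05 × 1.5 = −0.075 mg/dL. Over f = 2–10% and d = 1.5–2.0 it runs from −0.03 to −0.20.
- SD of the affected arm = √(s² + f(1−f)d²). For s = 0.6: √(0.36 + 0.0475 × 2.25) = 0.68. For s = 0.8: 0.86.
- Median shift, by simulation (3,000 runs): about −0.04 to −0.05 mg/dL.
- Average minimum, control v affected arm, by simulation: 7.2 v 6.4 mg/dL (s = 0.6) and 6.6 v 6.0 (s = 0.8). With s = 0.8 the control minimum was as low or lower in about 9% of runs.
- Subjects below 7.5, s = 0.6: control Φ(−1.5/0.6) = 0.0062, so about 3 of 450. Affected arm 0.95 × 0.0062 + 0.05 × 0.5 = 0.0309, so about 14 of 450.
- Subjects below 7.5, s = 0.8: control 0.0304, about 14. Affected arm 0.0539, about 24.

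So the mean and median barely move. The minimum and SD do respond, but the minimum describes one subject per arm and visit, and neither yields a count.

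**Step 3. How far a p-value depends on the assumed background.** Fisher exact test, 450 per arm, an excess of about 3 percentage points:

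| Background v raised | Counts | p |
|---|---|---|
| 1% v 4% | 4 v 18, or 5 v 18 | 0.004, or 0.010 |
| 2% v 5% | 9 v 22 | 0.027 |
| 5% v 8% | 22 v 36 | 0.08 |
| 10% v 13% | 45 v 58 | 0.21 |
| 15% v 18% | 68 v 81 | 0.28 |

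(1% of 450 is 4.5, hence the two entries.) The same excess runs from 0.004 to 0.28 according to a background rate that the documents do not give. No single p-value supports the point. Protocol 9.8 and SAP 2.7 do not plan routine safety testing in any case.

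**The case against.** The case for leaving the plan alone has four parts.

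- **The calcium risk is small on the documents' own account.** Protocol 2.4 ties hypocalcemia to citrate of 30% or more, regards the low concentration as safe even after an unintended bolus, and adds that rapid flushing is neither expected nor advised. Protocol 2.3 calls 3.5% citrate safe under worst-case assumptions. This stands. A reader might infer that the trial is hiding an expected calcium effect; nothing in the documents supports that.
- **The samples would miss a brief fall.** Citrate is expected to be metabolized within minutes, and calcium is drawn every four weeks. This stands too: a restored count would describe sustained low values, not a transient fall after a flush.
- **Clinically relevant abnormalities are already counted.** They should be recorded as adverse events and tabulated per subject. This stands in part. It narrows the gap to values that the investigator does not judge relevant, a judgement that may vary over up to 85 centers.
- **The data can still be displayed.** SAP 3.1 keeps unsummarized data available for ad hoc displays, and the minimum and SD are shown. So the tempting reading, that the trial cannot show or report low calcium at all, goes too far. But an ad hoc display chosen during report writing carries less weight than a table promised in the protocol.

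The change is also openly declared in the section meant for it. That makes it transparent but does not supply a reason.

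**Conclusion.** The point holds as a minor one, and the remedy is a cheap improvement. The plan deliberately removes the only unfiltered count of abnormal laboratory results and gives no reason. The laboratory summaries that remain can signal an extreme value but cannot say how many subjects in each arm lie outside limits. The TEAE tables count only what investigators judge clinically relevant.

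This rests on the text alone and on no assumed figure. The calcium arithmetic only illustrates why means and medians are a poor substitute. It does not show that an effect exists, how large it would be, or that a difference between arms would reach significance.

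**What to change.** Delete the laboratory exclusion from SAP Section 4. In SAP 3.8.3, which Addendum 1.2 already applies to the data through the last patient's last visit, add by arm the number and percentage of subjects with values below and above the laboratory reference range, at baseline and at the worst on-treatment value. An equivalent baseline-to-worst shift table would serve as well. Cover the hematology and chemistry tests already collected, including adjusted calcium. Give the number of subjects with a post-baseline value as the denominator, and present the table descriptively, without testing.

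The report should say that four-weekly samples reflect sustained rather than momentary changes. Any illustrative p-value should be left out, or shown as the full range over background rates.

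The cost is a small wording change and one or two more tables. No new data, visit or procedure is needed. Because the protocol already promised the count, restoring it is not a choice of analysis made after seeing results. If the sponsor prefers to keep the exclusion, SAP Section 4 should at least state why.
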